SQUASH	Short Questionnaire to Assess health-enhancing physical activity
THA	Total Hip Arthroplasty
UCLA	University of California at Los Angeles
UK	United Kingdom
WMO	Medical Research Involving Human Subjects Act; in Dutch: Wet Medisch-wetenschappelijk Onderzoek met Mensen

SUMMARY

Rationale:

Arthritis significantly impacts patients' lives, affecting everything from pain and fatigue to daily activities and overall mortality. Physical activity (PA), particularly moderate-to-vigorous physical activity (MVPA), is crucial in managing arthritis symptoms and reducing mortality risks, with even minimal MVPA providing significant health benefits. Wearable technology has revolutionized the measurement of physical activity, offering accurate, large-scale data that informs treatment efficacy. Despite this, little is known about how common arthritis treatments affect physical activity levels, highlighting a critical gap in our understanding. Joint replacement, while effective in reducing pain and improving function, shows varying long-term mortality outcomes, suggesting the need for further research into how different surgical procedures impact patients' activity levels and overall well-being.

Objectives: i) To compare the volume and intensity of physical activity 15 years after surgery in patients after hip resurfacing and total hip replacement and ii) to explore the association between the participants' physical activity and functional outcome scores.

Study design: A cross-sectional observational (follow-up) study.

Study population: We will approach patients that have previously participated in a randomised controlled trial during which they received either hip resurfacing ($n = 34$) or total hip replacement ($n = 26$).

Intervention (if applicable): In this study there is no intervention, only observation using accelerometers. Participants will be asked to complete four physical activity questionnaires. Subsequently, they will wear a tri-alaxial accelerometer on their non-dominant wrist continuously for ten days and nights, and simultaneously wear a tri-axial accelerometer taped to the surgical thigh for a period of 48 hours.

Main study parameters/endpoints: Using the accelerometers we will measure the participants' physical activity energy expenditure (PAEE), the intensity distribution of PAEE and step count. Secondary outcomes include self-reported physical activity, health status and the ability to perform specific activities.

Nature and extent of the burden and risks associated with participation, benefit and group relatedness: There is no risk associated with participating in this study. Patients will be asked to complete four paper questionnaires at home (duration: 15 minutes). Patients will also be asked to wear an accelerometer on their wrist for ten days, and to simultaneously wear one accelerometer on their surgical thigh for 48 hours. The accelerometers collect physical activity data automatically.

1. INTRODUCTION AND RATIONALE

1.1 Arthritis and physical activity

The impact of arthritis is wide-ranging and patient specific. From traditional symptoms such as fatigue and pain to more holistic considerations like holiday destination and pragmatism over style(1), arthritis affects many patient life domains. Treatment strategies are similarly broad - spanning lifestyle changes, medicine, and surgery - as is the definition of what constitutes success in treatment. Surveys of arthritis sufferers have identified a reduction in fatigue, pain and a return to normal activities as core expectations of this patient group(1),(2), but again, answers are highly personal. Yet beyond commonly reported symptoms, some forms of arthritis are associated with a shortened life span. For example, a 15-year prospective study of rheumatoid arthritis patients in the Netherlands revealed significantly higher all-cause mortality in rheumatoid patients (3). Likewise, lower limb osteoarthritis is associated with increased cardiovascular mortality (4) and all-cause mortality (5). Further, gait speed, which commonly decreases with end-stage arthritis, independently predicts mortality in the elderly (6). Recent population-based studies suggest that a lack of physical activity may explain, at least in part, these findings. Physical activity researchers are ever more aware of the importance of physical activity volume and intensity in healthy ageing, both for all-cause mortality and intermediate disease states (7),(8),(9),(10),(11),(12). In a population-based study of over 96,000 participants, Strain et al. demonstrated that physical activity volume and intensity are independently associated with all-cause mortality (7). Figure 1 illustrates this relationship, but it also highlights the additional benefit of accumulating a greater fraction of physical activity energy expenditure (PAEE) from moderate-to-vigorous physical activity (MVPA).

[figure not shown]

Figure 1. PAEE, intensity and all-cause mortality (7).

This study (7) demonstrated participants with the lowest levels of PAEE had almost double the mortality risk of those with average levels of physical activity. Even at low levels of physical activity, those with 20% MVPA had a 30% lower mortality rate than those with 10% MVPA. For context, this is the equivalent of a 12-minute stroll versus a brisk 7-minute walk. These findings are further supported by the results of a systematic review and meta-analysis of 30 million participants, confirming that significant protection against chronic disease is derived from just 10 minutes of MVPA per day (9). Further population-based studies have demonstrated similar associations with intermediate disease states, including obesity and cardiometabolic risk score, along with depression and anxiety (8),(12),(13). Given the sweeping benefits of physical activity, it is perhaps not surprising that markers of physical activity such as 'performing daily activities with ease', frequently rate second to pain and/or fatigue in studies of patient hopes for arthritis treatment (1),(2),(14),(15). By logical extension, it is evident that for a notable proportion of arthritis patients, treatment can only be successful if it empowers that patient to achieve their desired level of activity. Despite this, relatively little is known about the effect of common arthritis treatments on levels of physical activity. Even less is known about the intensity distribution of patients following treatment. This represents a core knowledge gap in our evaluation of the treatments provided.

1.2 Wearables and physical activity

Until the introduction of wearables, physical activity was difficult to measure objectively or at scale. Traditionally, PA was studied using subjective measures such as surveys or diaries, or extremely expensive or intrusive objective measures such as doubly labelled water (DLW) or indirect calorimetry (16),(17),(18). The former methods can be applied in large population cohorts but are known to be subject to bias (17),(19). The latter provide highly accurate information about energy expenditure but provide no information about the underlying energy distribution (intensity) of that energy expenditure (20).

The advent of wearable technology has revolutionised the study of physical activity at a population level. A variety of estimation techniques, ranging from uniaxial accelerometers to combined heart rate and movement sensors, have been used to study a diverse range of population cohorts (11),(21),(22),(23),(24). As a result, physical activity researchers have been able to look beyond simple metrics like time in MVPA to more biologically based phenomena. This has seen a shift from descriptive to aetiological studies that link an individual's average daily PAEE, or their underlying intensity composition, with disease states (25),(26),(27).

Of the methods currently available, triaxial accelerometers such as the GENEActive Device (Activinsights, UK; Figure 2) are emerging as a favoured device amongst physical activity researchers. Compared to other methods, the devices are well tolerated, can be placed on a variety of sites throughout the body, are worn 24 hours a day, are relatively inexpensive,

reusable, and are validated against the gold standard DLW in a British population (22),(28). Furthermore, as wrist-worn devices, they are suitable for use in orthopaedic patients with previous lower limb arthroplasty. Alternative devices include the thigh-worn Axivity AX3 3-Axis Logging Accelerometer (Axivity, UK; Figure 3). These are versatile, lightweight devices that have been validated against other monitors (29).

Figure 2. GENEActive triaxial accelerometer (Activinsights, UK)

[figure not shown]

Figure 3. Axivity AX3 3-Axis Logging Accelerometer (Axivity, UK)

1.3 Physical activity and common treatments for severe arthritis

Joint replacement is widely heralded as a safe and effective option for patients with end-stage arthritis, as patients report improved function and less pain. However, the statistic used to describe the success of the procedure is that of 'implant survival', which specifically ignores the more important metric of 'patient survival' (30). The two graphs below, from the National Joint Registry of England and Wales, illustrate this paradox: Figure 3A shows the unattractive higher mortality risks associated with total knee replacement, while Figure 3B shows the attractive low risk of revision surgery for the procedure.

[figure not shown]

Figure 3. Implant and patient survival post-knee replacement (30).

In earlier work from our group, we have published the substantial differences in gait characteristics between patients with different types of surgical procedures (31),(32),(33). However, any extrapolation from these small laboratory-based studies would be theoretical. Our best explanation for the profound difference in mortality, in the longer term, between more and less radical procedures is that patients who are allowed to retain more of their own bodies feel more normal and thus enjoy more activity. Alternatively, patients with large stiff metal implants substituting large parts of their femur and tibia are not expected to feel 'normal' ever again. To test this explanation, we propose to study physical activity of two groups of patients who participated in a previous study (34). In the current study, we want to explore whether physical activity levels varies between these two groups 15 years after their index surgery.

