4. STUDY POPULATION

We will only approach patients that have participated in a previous randomised controlled trial (34) that was conducted in Rijnstate hospital between 2007-2008. These include 34 patients after hip resurfacing and 26 patients after total hip replacement.

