8.2 Randomisation, blinding and treatment allocation

In this observational (follow-up) study participants will not be randomised, blinded or treated. The potential participants for this current study have previously participated in a randomised controlled trial. In this RCT (34), a total of 82 patients were randomly assigned to receive resurfacing hip arthroplasty (RHA, $n = 34$) with a 6-mm thick cobalt-chromium cup or conventional total hip arthroplasty (THA, $n = 26$) with a more conical threaded titanium cup. All participants of this previous RCT will be contacted to ask if they are willing to participate in this follow-up study.

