11.2 Recruitment and consent

Participants will be approached by their treating orthopedic surgeon using an introduction letter and a Patient Information Form (PIF) which includes the Informed Consent Form (IC, see Appendix E). One week after sending the PIF/IC, the coordinating researcher will contact the patient by phone to ask whether the patient has any questions about the study, and whether he/she is willing to participate. No pressure will be placed on any individual to participate; it will be made clear that participation is entirely voluntary and that participation can cease at any time. Participants who are will be asked to sign and date the Informed Consent form and return it to the researcher in a pre-paid envelope.

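### Section 1.3 offers the activity comparison as a test of a mortality explanation, but the study measures activity once, in surviving and consenting RCT participants, and has no mortality outcome

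*Combined protocol and SAP*

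**What the plan says.** Section 1.1 reports from a population cohort that "participants with the lowest levels of PAEE had almost double the mortality risk of those with average levels of physical activity". Section 1.3 refers to "Our best explanation for the profound difference in mortality, in the longer term, between more and less radical procedures" and proposes that patients who keep more of their own anatomy feel more normal and are therefore more active. It continues: "To test this explanation, we propose to study physical activity of two groups of patients who participated in a previous study (34".

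The sampling frame is closed. Section 4 says "We will only approach patients that have participated in a previous randomised controlled trial" and adds "These include 34 patients after hip resurfacing and 26 patients after total hip replacement". Section 8.2 says "All participants of this previous RCT will be contacted to ask if they are willing to participate in this follow-up study", and section 11.2 says "it will be made clear that participation is entirely voluntary". The source RCT ran in 2007-2008, and activity is measured once, some 15 years after surgery.

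Section 8.2 also states that "a total of 82 patients were randomly assigned to receive resurfacing hip arthroplasty" or conventional total hip arthroplasty, with arm sizes of 34 and 26.

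The analysis in section 10.1 starts from returned devices. It names no model for the between-arm difference. Age, sex and BMI appear there only in a sentence on differential bias, next to the model-performance metrics. Section 12.1 lists age, gender, BMI, comorbidity and medication among the data taken from the records, but not vital status or RCT baseline data. No section plans to count deaths or refusals by arm, to compare participants with non-participants, or to limit the conclusion to survivors.

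**The concern.** The explanation in section 1.3 has two links: from procedure to activity, and from activity to mortality. The design can speak only to the first. Even there it observes people selected by two events that follow randomisation, survival and consent. If the authors' reasoning is right, both procedure and activity affect who is still alive. Willingness to wear two devices may also go with activity. A comparison restricted in this way is no longer fully protected by the RCT allocation.

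What is at stake is the conclusion. A null result could be taken as evidence against the explanation, and a positive one as support for it, when neither settles a question about mortality. Without counts by arm, a reader cannot judge how much selection took place.

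**Working it through.** **1. The plan's own figures.** 34 + 26 = 60, against 82 stated as randomised. The gap is 82 − 60 = 22 patients, and 22/82 = 26.8%. The documents do not say who these patients are. The starting number for any account of deaths and refusals is therefore unclear. There is no sample size, SD or effect size in the documents to reproduce.

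**2. Precision, for scale.** In units of the between-patient SD, SE = √(1/n₁ + 1/n₂).
- All 60 measured: √(1/34 + 1/26) = 0.26 SD.
- Consent 50% in RHA and 80% in THA (17 and about 21): 0.33 SD.
- Consent 80% in RHA and 50% in THA (about 27 and 13): 0.34 SD.

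**3. Deaths.** The documents give no hip-specific mortality by arm, so these inputs are assumptions. Activity is normal with SD 1, mean 0 in THA and 0.5 in RHA. Survival to measurement is exp(−H·exp(−b·activity)), with H = −ln(1 − m) and m the mortality at activity 0. The near-doubling in section 1.1 is spread over 1 SD (b = ln 2 = 0.693) or 2 SD (b = 0.347) of lower activity. Numerical integration gives the mean difference among survivors:

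| Hazard doubles per | m = 20% | m = 30% | m = 40% |
|---|---|---|---|
| 1 SD | 0.455 | 0.435 | 0.417 |
| 2 SD | 0.488 | 0.481 | 0.473 |

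The loss is 0.50 − 0.488 = 0.012 SD at best and 0.50 − 0.417 = 0.083 SD at worst, about 2% to 17%. The SD among survivors shrinks too. In survivor-SD units the difference is 0.46 to 0.49, a loss of about 1% to 9%.

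These figures let death act only through activity. A separate simulation used a hazard ratio of 1.5 or 2.0 per SD and 90%, 80% or 65% survival at mean activity, and added a direct hazard ratio of 1.5 for THA. A true 0.50 SD then became 0.32 to 0.47 SD. A true zero became −0.02 to −0.11 SD, which is against resurfacing.

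**4. Consent.** If willingness correlates r with activity and a proportion p of an arm consents, that arm's mean rises by r·φ(z_p)/p. The factor φ(z_p)/p is 0.798 at p = 50%, 0.644 at 60%, 0.497 at 70% and 0.350 at 80%. With no true difference:
- 50% v 80%: r = 0.5 gives 0.5 × (0.798 − 0.350) = 0.22 SD; r = 0.3 gives 0.13 SD.
- 60% v 70%: r = 0.5 gives 0.5 × (0.644 − 0.497) = 0.07 SD; r = 0.3 gives 0.04 SD.

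The arm with the lower consent rate looks more active, so the shift can favour either arm. Equal consent rates with equal r give no shift.

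**5. Comparison.** The worst shift from deaths through activity (0.08 SD), the worst with the added direct effect (0.50 − 0.32 = 0.18 SD) and the worst from consent (0.22 SD) each lie below 0.26 SD. The consent figure belongs with the SE of 0.33 to 0.34 SD that goes with those consent rates.

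**The case against.** The strongest reply is that most of the plan is worded with care. The primary objective is to compare, section 1.3 itself goes on to say that the authors want to explore whether activity varies, and section 3 calls the design cross-sectional and observational. A reader might infer that the plan treats the survivor contrast as the causal effect of the procedure. The documents do not support that: the claim to test the explanation is one clause in the introduction. This reply stands, and it limits the point to that clause and to the missing statement of scope.

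A reader might also infer that the least active patients, and more of them after total hip replacement, have already died. That too is unsupported. The registry graphs in section 1.3 concern knee replacement, the near-doubling of risk comes from a general population cohort, and no mortality by arm is given for these hips. It is the authors' hypothesis, not a documented fact about this cohort.

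Nor does survivor selection, under the stated mechanism, manufacture a benefit of resurfacing; it pulls the difference towards zero. Consent gaps as wide as 50% v 80% are assumed. Section 11.2 describes the same letter and telephone call for everyone, and nothing in the documents suggests such a gap.

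Finally, restriction to survivors is unavoidable, because activity at 15 years does not exist for those who died. That is correct. It is a reason to state the restriction, not to leave it unsaid.

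**Conclusion.** The point holds in limited form. The sentence in section 1.3 claims more than the design can deliver, and the plan neither acknowledges nor describes the selection by survival and consent. The probable bias is modest: about 0.01 to 0.08 SD towards zero from deaths acting through activity, and about 0.04 to 0.22 SD in either direction from differential consent, each smaller than one standard error. Imprecision is the larger problem in a sample of at most 60. All mortality, correlation and consent inputs are assumptions; the structural conclusion does not depend on them. The change is worth making because it alters what the study may conclude and costs little. The documents do not support a claim that the comparison is invalid or that its result will be wrong in a known direction.

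**What to change.** - **Section 1.3.** Replace the clause that announces a test of the explanation. Say that the study describes activity among surviving, consenting former RCT participants and does not test the mortality explanation. Limit the conclusions to match.
- **Section 10.1.** Specify the RHA-THA difference in PAEE, its intensity distribution and step count, with a confidence interval, adjusted for age and sex. Both are already collected under section 12.1. State that this adjustment only partly addresses selection.
- **Section 8.2.** Reconcile 82 randomised with 34 + 26 = 60. Then report by randomised arm the numbers randomised, dead, untraceable, declining and measured, as far as METC approval allows use of non-participants' data.

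I would not add an analysis that ranks the deceased below every measured value. It mixes mortality into the activity endpoint and conflicts with confining the claim to survivors.

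The cost is a few sentences of protocol text, one pre-specified model and one table. The downsides are a narrower stated conclusion and a possible need for METC coverage of non-participants' vital status, which section 12.1 does not list. That is best settled before recruitment.

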2. OBJECTIVES

2.1 Primary Objective:

To compare the volume and intensity of physical activity 15 years after surgery in patients after hip resurfacing and total hip replacement.

2.2 Secondary Objective(s):

To explore the association between the participants' physical activity and functional outcome scores.

3. STUDY DESIGN

This is a cross-sectional observational (follow-up) study in which we will ask participants to complete four paper questionnaires, wear a tri-axial accelerometer on their non-dominant wrist continuously for ten days and nights, and simultaneously wear a tri-axial accelerometers taped to the surgical thigh for a period of 48 hours.

4. STUDY POPULATION

We will only approach patients that have participated in a previous randomised controlled trial (34) that was conducted in Rijnstate hospital between 2007-2008. These include 34 patients after hip resurfacing and 26 patients after total hip replacement.

5. TREATMENT OF SUBJECTS

N/A.

6. INVESTIGATIONAL PRODUCT

N/A.

7. NON-INVESTIGATIONAL PRODUCT

During this study, the participants will be asked to continuously wear two different types of accelerometers that will measure their physical activity.

GENEActiv triaxial accelerometer (wrist-worn)

We will ask the participants to wear the GENEActiv triaxial accelerometer (Activiinsights, UK) on their wrist for ten consecutive days and nights. The GENEActiv is currently a Class I self-certified medical device under the MDD 93/42/EEC for CE Marking. GENEActiv is transitioning to the new Medical Device Regulation (EU) 2017/745 in 2023. Under the MDR the GENEActiv will become a Class IIa medical device.

Axivity AX3 Logging tri-axial accelerometer (thigh-worn)

We will also ask the participants to wear an Axivity AX3 Logging tri-axial accelerometer taped to the surgical thigh for a period of 48 hours. This accelerometer conforms to several EU regulation directives (89/336/EEC Electromagnetic Compatibility Directive, amended by 92/31/EEC & 93/68/EEC 72/23/EEC Low Voltage Equipment Directive, amended by 93/68/EEC). The product also meets the following standards: EN61326-1:2006 Electrical Equipment for Measurement, Control and Lab use, Radiated Emissions EN 55011:1998 A1 A2, Electrostatic Discharge EN 61000/4/2:1995 A1 A2 and Radiated Immunity EN 61000/4/3:2002.

Both types of accelerometers have been deemed safe to use on the following basis:

- They have a self enclosed, non-replaceable, 3.7V Lithium Polymer Cell.
- The products have no sharp edges.
- The products do not contain explosive, toxic or volatile parts.

All the relevant testing has been completed to ensure the device complies to the above standards. The technical documentation required to demonstrate that the product meets the requirements of the Low Voltage Directive is available for inspection by the relevant enforcement authorities. The Axivity AX3's CE mark was first applied in December 2011.

